6.1.2 Exclusion Criteria

Patients who meet any one of the following criteria must be excluded:

- Participation in any other investigational study that may interfere with interpretation of the Registry results
- Incessant ventricular tachycardia (VT) and/or documented spontaneous, frequently recurring VT that is reliably terminated with anti-tachycardia pacing
- Patients with unipolar pacemakers or implanted devices that revert to unipolar pacing

7.0 Methods

7.1 Visit Schedule

Table 3 documents the information that will be requested at each visit.

Table 3: Summary of Information Requested at Each Follow-Up

	Enrolment	Implant	Scheduled FU	Unscheduled FU	Annual FU
Informed Consent	x				
Demographics & Medical History	x		x	x	
VT/VF Defibrillation Testing		x ^A	x ^A	x ^A	
Induced Episodes		x ^A	x ^A	x ^A	x ^A
Spontaneous Episodes		x	x	x	x
Clinical Events & Hospitalizations		x	x	x	x
Deaths	x	x	x	x	x
Withdrawals	x	x	x	x	x
Adverse Events	x	x	x	x	x

^A If done

7.2 Enrolment

Patients may not be enrolled in the Registry until the investigator receives “Approval to Enrol” from the sponsor. Patients are considered enrolled after providing written informed consent in accordance with applicable local and national guidelines and/or Ethics Committee (EC) requirements.

7.2.1 Enrolment Data

Patient demographics, including age, height, weight, medical history, cardiovascular disease diagnoses and device indications will be collected for all enrolled patients. A pre-operative screening ECG for prospective patients should also be available. Table 4 lists the data that will be requested at the Enrolment visit.

Table 4: Enrolment Data Collection

Data Collection	Retention of Originals
Patient Consent Form Demographics (Physical) and Medical History including cardiac medications	Investigational Centre
Pre-operative ECG screening	Investigational Centre and e-Copy to Boston Scientific, if requested

7.3 Implant

7.3.1 Implant Procedure

The clinical investigator is responsible for implanting, testing, and programming the S-ICD System and using the standard of care methods established by the investigational centre (e.g. sterile technique, personnel required, etc.). Refer to the S-ICD System User’s Manual for detailed instructions regarding the implantation and use of the S-ICD System.

7.3.2 Acute Defibrillation Testing

After implanting the S-ICD System, a ventricular arrhythmia can be induced using the S-ICD pulse generator, a temporary endocardial pacing catheter, or an alternative induction method at the discretion of the investigator. If conversion testing is performed during the initial implant procedure (or at any subsequent follow-up-scheduled or unscheduled) the following definitions will be applied to the testing with respect to data collected on the case report form:

- A *successful conversion* is defined as any shock delivered by the S-ICD pulse generator that terminates the induced VT/VF arrhythmia (device declared end of episode) and does not require an external defibrillator. This includes episodes where VT/VF converts but an atrial tachyarrhythmia may persist.
- A *failed conversion* is defined as the need for an external defibrillator following the inability of the S-ICD pulse generator to convert the VT/VF arrhythmia.
- An *attempt* is defined as an induction resulting in VT/VF that does not receive therapy (most probably due to the rhythm breaking prior to delivery of shock) and/or an induction not resulting in VT/VF.

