3.2.1 Observational Data Collection

When available, descriptive statistics will be used to present observational data to further characterize the performance of the S-ICD system. This can include (but is not limited to):

- Clinical Indications for implant
- Patient demographics
- Type of anesthesia/analgesia
 - General anesthesia/local anesthesia/conscious sedation etc.
- Implant procedure duration
- Use of fluoroscopy and X-Ray
- Induced Shock Conversion Efficacy
 - Defined as any shock delivered by the S-ICD pulse generator that terminates the induced arrhythmia and does not require an external defibrillator.
- Spontaneous Shock Conversion Efficacy
 - Defined as any shock delivered by the S-ICD pulse generator that terminates the spontaneous arrhythmia (device defined end of episode)
- First Shock Conversion Efficacy
 - Defined as the percentage of successful conversions (device defined end of episode) caused by the first shock delivered by the S-ICD pulse generator. Data will be evaluated for both induced and spontaneous episodes
- All cause therapy (appropriate and inappropriate)
 - Inappropriate therapy is defined as delivery of shock therapy for any rhythm other than VT/VF.
- Total Shock Burden
 - Defined as the total number of therapies delivered (both appropriate and inappropriate) divided by the total number implanted patients
- Complication rates over time
- Frequency of scheduled and unscheduled follow-ups/hospitalizations
- All cause mortality
- Length of hospital stay
 - Where possible, hospital stay lengths will be calculated for implant procedure as well as scheduled and unscheduled follow-ups

- All clinical events
- Clinical event rates over time
- QOL Assessments
 - Patients will complete a brief set of standardized QOL questionnaires at baseline (pre-implant), 3 months post-implant, 6 months post-implant and 12-months post implant (see section 7.8) with the intention of comparing scores with a transvenous ICD cohort
- Hospital personnel implant and Follow-Up Experience (using an optional survey to be completed at two time points)

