5.5 Additional Data Analysis

- Conversion efficacies for both induced and spontaneous episodes and first shock will be summarized as the number of subjects and the percentages relative to the Registry population including the corresponding 95.0% two-sided exact binomial confidence interval.
- Clinical event rates will be presented as 30-day event rates as summarized by number of subjects and its corresponding percentage and 95.0% two-sided exact binomial confidence interval and long-term rates as either linear rates or Kaplan-Meier freedom from event.
- Linearised rate of inappropriate therapies will also be calculated by dividing the total number of inappropriate therapies by the total number of follow-up patient years. Linearised rate calculation will only be initiated if a minimum of 100 patient years have been reached.
- Kaplan-Meier estimates and curves for therapy delivered including:
 - Time to first therapy delivered (both appropriate and inappropriate)
 - Time to first appropriate therapy delivered
 - Time to first inappropriate therapy delivered
- Re-occurrence of inappropriate shock therapy after reprogramming will be calculated using the total number of additional inappropriate shocks recorded from patients who have previously experienced at least one inappropriate shock and had their S-ICD reprogrammed in an attempt to resolve the issue (adjustments may include but are not limited to, changing sensing vector, adjustment to ECG gain, reprogramming of shock rates)
- Considering that patients who are prospectively enrolled in this Registry will come from the investigator's general ICD population, it is a priori unknown how many will be primary versus secondary prevention patients. Analyses will be conducted for primary versus secondary prevention, for inclusion in separate cost-effectiveness models for those populations.

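### The induced-test classes in Section 7.3.2 overlap and leave a gap, so a failure of the S-ICD to sense, treat or convert induced VT/VF need not be recorded as a failed conversion

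*Combined protocol and SAP*

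**What the plan says.** Section 7.3.2 (Acute Defibrillation Testing) covers conversion testing at implant or at any follow-up. It says that "the following definitions will be applied to the testing with respect to data collected on the case report form". There are three classes:

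- A *successful conversion* "is defined as any shock delivered by the S-ICD pulse generator that terminates the induced VT/VF arrhythmia", with the end of the episode declared by the device and no external defibrillator needed.
- An *attempt* "is defined as an induction resulting in VT/VF that does not receive therapy". A bracket and a second branch follow: "most probably due to the rhythm breaking prior to delivery of shock) and/or an induction not resulting in VT/VF".
- A *failed conversion*, by contrast, "is defined as the need for an external defibrillator following the inability of the S-ICD pulse generator to convert the VT/VF arrhythmia".

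Section 3.2.1 describes Induced Shock Conversion Efficacy as follows: "Defined as any shock delivered by the S-ICD pulse generator that terminates the induced arrhythmia and does not require an external defibrillator". It gives no denominator and does not mention attempts. Under Section 5.5, conversion efficacies "will be summarized as the number of subjects and the percentages relative to the Registry population", with a 95% exact binomial interval. Table 3 in Section 7.1 marks defibrillation testing as recorded only if done. Conversion efficacy is not among the three Registry endpoints in Section 3.2.

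**The concern.** A test in which VF was induced and the device did not sense it, or did not deliver a shock, is a device failure. Section 9.1 lists failed and delayed delivery of therapy among the risks, and Section 2.0 cites complete detection of induced episodes as evidence for the system. A classification for induced tests should therefore place such a test unambiguously among the failures. The one in Section 7.3.2 does not.

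The code chosen at the site carries unusual weight here. Section 4.4 guarantees adjudication only for endpoint-related events and episodes, so central review need not look at induced tests. Appendix A (Episode History) says that an episode begins at capacitor charging and that arrhythmias ending before charging are not kept. Undersensed VF may therefore leave no stored episode, and the case report form may be the main record of what happened.

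**Working it through.** **Step 1: put the possible tests against the three definitions.**

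| Induced test | Successful | Failed | Attempt |
|---|---|---|---|
| No VT/VF induced | no | no | yes |
| VT/VF ends by itself before a shock is due | no | no | yes |
| VT/VF not sensed or not treated, ends without an external shock | no | no | yes |
| VT/VF not sensed or not treated, external rescue | no | yes | yes, if therapy means device therapy |
| S-ICD shock ineffective, external rescue | no | yes | no |
| S-ICD shock ineffective, VT/VF then ends by itself | no | no | no |
| S-ICD shock ends VT/VF | yes | no | no |

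The bracket in the attempt definition names a likely cause. It does not limit the class to that cause, so row 3 is an attempt on the wording. Row 4 fits two classes, because failed conversion does not require that an S-ICD shock was delivered. Row 6 fits none, and it can occur because Appendix A allows up to five shocks per episode. The classes are thus neither exclusive nor exhaustive.

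**Step 2: follow the class into the analysis.** No section says whether attempts enter the efficacy percentage. There are two possibilities.

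*Literal Section 5.5 denominator (Registry population).* A subject coded as an attempt stays in the denominator as a non-success, so dropping does not arise. Assume, for illustration, that 900 of the 1000 target patients are tested once each, with 9 failures after shocks and 9 untreated VF. Either coding gives 882/1000 = 88.2%. The 100 untested patients are then counted as not converted, which is hard to interpret as a conversion efficacy.

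*Tested denominator with attempts dropped.* Here the coding matters, and step 3 gives the size.

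**Step 3: size if attempts are dropped.** The plan states no conversion efficacy to reproduce. The interval method is the exact binomial named in Section 5.5. As a check, it gives -7.6/+5.1 points at 90% with n=100 and -1.1/+0.8 at 98% with n=900, matching Table 1.

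Inputs:
- N = 900 inductions with VT/VF (assumed; the largest size in Table 1).
- f = 9 failures after S-ICD shocks, i.e. 1% (assumed).
- u = untreated VF, 0.5% to 2.35% of N (assumed). The top of the range is the exact upper 95% limit for non-detection when all 155 induced episodes were detected (Section 2.0): 1 - 0.025^(1/155) = 2.35%.

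With s = N - f - u successes, efficacy is s/(N - u) if untreated VF is coded as an attempt and dropped, and s/N if it is counted as failure.

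| u | Dropped | Counted as failure (95% CI) | Difference, points |
|---|---|---|---|
| 4 (0.5% = 4.5, taken as 4) | 887/896 = 99.00% | 887/900 = 98.56% (97.5 to 99.2) | 0.44 |
| 9 (1%) | 882/891 = 98.99% | 882/900 = 98.00% (96.9 to 98.8) | 0.99 |
| 18 (2%) | 873/882 = 98.98% | 873/900 = 97.00% (95.7 to 98.0) | 1.98 |
| 21 (2.35% = 21.15, taken as 21) | 870/879 = 98.98% | 870/900 = 96.67% (95.3 to 97.7) | 2.31 |

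When dropped, the estimate stays near 99.0% however many untreated cases there are. From about 1% untreated VF, the difference is as large as one arm of the exact interval at that sample size.

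**The case against.** The strongest reply is that the classes work when read sensibly. The bracket shows that attempt is aimed at rhythms that break before the shock. The definition says therapy, not device therapy, so externally rescued VF has arguably received therapy and belongs under failed conversion, whose wording covers it. This stands in part: a reader might infer that every untreated induced VT/VF goes to attempt, and the documents do not support that. What remains is an overlap without a precedence rule for rescued cases, plus untreated VT/VF that ends without rescue and is an attempt on the wording.

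A reader might also infer that the plan removes attempts and so overstates efficacy. No section says so, and Section 5.5 uses the Registry population. That part of the reply stands. It does not settle the matter, because testing is optional and a meaningful percentage needs a tested denominator, for which the plan has no rule on attempts.

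The only detection figure in the documents is 155 of 155 induced episodes, which gives no direct evidence that non-detection is common. It does not show a zero rate either, hence the upper limit used above.

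Finally, a reader might infer that the spontaneous measure credits the device with external rescues, since it lacks the external-defibrillator clause. Its definition reads "Defined as any shock delivered by the S-ICD pulse generator that terminates the spontaneous arrhythmia (device defined end of episode", so an S-ICD shock must still be what ended the rhythm. Adding the clause would only clarify.

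**Conclusion.** The defect in the classification is established from the text alone. Induced VT/VF that the S-ICD fails to sense or treat can be coded as an attempt, the rescued cases fit two classes, and one kind of failed shock fits none. Failures can go uncounted, and coding can differ between sites.

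The effect on reported efficacy is conditional. It is about 0.4 to 2.3 points if attempts are dropped and if 0.5% to 2.35% of induced VF goes untreated and is all coded as attempt. Both conditions are assumptions. Under the literal Section 5.5 denominator there is no inflation from dropping.

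The reach is limited to the descriptive induced conversion measures, including induced first-shock efficacy. The three Registry endpoints and the sample-size tables do not use these classes. The point merits correction because the change is cheap.

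**What to change.** Change the data definitions, not the conduct of testing:

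1. Restrict *attempt* to (a) no VT/VF induced, or (b) VT/VF that ended by itself before shock delivery was due.
2. Give *failed conversion* precedence. Let it include VT/VF in the programmed therapy zone that was not sensed or not treated, and S-ICD shocks that did not end the rhythm, whether or not an external defibrillator was used.
3. Add a separate *non-evaluable* class for VT below the programmed zone, or VT ended by pacing before therapy was due. Otherwise a device that behaved as programmed would be scored as a failure.
4. In Section 5.5, base induced efficacy on tested subjects with evaluable induced VT/VF. Report the numbers of attempts and non-evaluable tests by reason.
5. Optionally, repeat the external-defibrillator clause in the spontaneous definition of Section 3.2.1 for consistency.

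The cost is revised case report form text, a few definitions and a small amount of recoding. Reported efficacy may be slightly lower. Past tests should be reclassified from the site notes and worksheets on inductions (Table 5, Section 7.3.5) where available. Device printouts alone will not suffice, because undersensed episodes may not be stored and Table 5 data are requested only if available. Tests that cannot be reclassified should be counted and reported as such.

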7.3.3 Initial Device Set-Up and Programming

All device programming is at the discretion of the Investigator.

7.3.4 X-Ray Documentation of System Position

Any X-ray images that are obtained to document the final positioning of the S-ICD pulse generator and subcutaneous electrode will be collected.

7.3.5 Implant Data

Table 5 lists the data that will be requested from the implant procedure if available.

Table 5: Implant Data Collection

Data Collection	Retention of Originals
Medications (antibiotics; type of anesthesia etc.) Clinical events including System related complications, major cardiac procedures, Hospitalizations and deaths Medical notes/worksheets documenting implant time; use of fluoroscopy, VT/VF inductions etc.	Investigational Centre
S-ICD programmer printouts: Initial and Final Summary Reports Captured S-ECG Implanted Product and accessories utilized for S-ICD System (model/serial/lot/batch/etc.) Chest X-ray(s), if applicable SD Card, if applicable	Investigational Centre and e-Copy to Boston Scientific, if requested Boston Scientific (e.g. via CAMELION)

7.4 Scheduled Follow-ups up to 360 Days Post Implant

All scheduled device check follow-ups for at least 360 days post implantation date should be recorded. It is generally not necessary to separately report pre-discharge visits and wound checks unless any of the following have occurred:

- Spontaneous episodes that have not been previously reported
- Programming changes have been made to the implanted S-ICD System (e.g. reprogramming, performing auto set-up, template formation, vector/gain settings, etc.)
- Clinical events

If a patient’s follow-up schedule doesn’t include an exact 360 day (“12 month”) post implant visit, the nearest equivalent should be used such that each patient has at least 360 days of data.

7.4.1 Device Programming and Data Collection

All programming is at the discretion of the Investigator. Table 6 lists all the data that will be requested from scheduled follow-ups if available.

Table 6: Follow-Up Data Collection

Data Collection	Retention of Originals
Cardiac Medications Clinical events including System related complications, major cardiac procedures, Hospitalizations and deaths	Investigational Centre
S-ICD printouts: Initial and Final Summary Reports Captured S-ECG Spontaneous Episodes ± therapy Chest X-ray(s) if applicable SD Card if applicable	Investigational Centre and e-Copy to Boston Scientific, if associated with endpoint data Boston Scientific (e.g. via CAMELION)

7.5 Annual Follow-Ups

After all scheduled and unscheduled follow-ups have been collected for the first 360 days of the Registry, data will continue to be collected once annually until either 60

months of patient data have been collected; the patient withdraws from the Registry (or is withdrawn including for reasons of death) or is Lost to Follow-Up.

To aid with centre planning, this annual follow-up should be timed to occur 24, 36, 48 months +/- 90 days and 60 month +90 days post implantation date. Once a patient has a follow-up time of at least 1800 days post implant date they will have completed the study.

All the system-related events and hospitalizations that occurred during the period prior to the annual data follow up, will be collected.

7.5.1 Device Programming and Data Collection

All programming is at the discretion of the Investigator. Table 7 lists all the data that will be requested from annual follow-ups if available.

Table 7: Annual Follow-Up Data Collection

Data Collection	Retention of Originals
S-ICD printout: Initial and Final Summary Report Clinical events including System related complications, Major cardiac procedures, Hospitalizations and deaths Spontaneous Episodes ± therapy Current status of S-ICD system	Investigational Centre and e-Copy to Boston Scientific, if associated with endpoint data

7.6 Unscheduled Follow-up Visits

During the initial 360 day post implant period of data collection, physician office visits, emergency room visits, outpatient hospital visits, and hospitalizations related to the S-ICD System that occur in between scheduled, standard of care follow-up visits should be recorded as an unscheduled follow-up visit. Routine medical visits, unrelated to the S-ICD System do not need to be reported as additional follow-up visits.

If available, the following data should be collected from unscheduled follow-up visits:

- Clinical Events including details of any hospitalizations
- Device Evaluation including printouts of spontaneous episodes
- Chest X-rays

7.7 System Revisions

In the event that any component of the S-ICD System is surgically revised after the initial implant procedure, an additional implant form can be used to record changes to the system. Devices that are explanted, implanted or any additional conversion testing performed can be reported.

7.8 Quality of Life Assessments

Prospective patients enrolled in the Registry, aged ≥ 18 yrs of age and with sufficient understanding of the local language to effectively complete the set of questions, will be given the option to provide assessments of their QOL by completing the following short set of standardized and validated questionnaires:

- Short Form Health Survey (SF 12)
- Florida Patient Acceptance Survey (FPAS)
- Patient ICD Concerns Questionnaire (ICDC)
- Hospital Anxiety and Depression Scale (HADS)
- Type D Scale (DS14)
- EQ-5D

The questionnaires will be given to the patients in local language at baseline and approximately 3 months, 6 months and 12 months post-implant. Patients without a scheduled follow-up falling within these windows will have the questionnaires mailed to them in a pre-paid envelope. A reminder system will be implemented to follow-up on the status of mailed questionnaires. Prior to the mailing of follow-up questionnaires, the survival status of the patient should be checked.

QOL questionnaires will be returned to and analysed by:

[name] PhD
Professor of Cardiac Psychology
University of Southern Denmark
Institute of psychology
[name]
[name]
Denmark
[contact]

7.9 Implant and Follow-Up Experience Questionnaires

A survey will be used to document the experiences of the personnel implanting and performing the follow-ups of S-ICD patients at the participating centres. Implant experience questionnaires should be completed by the implanting physicians at each centre at two time points: 1) first prospective enrolment/implant and 2) end of Registry.

Follow-Up questionnaires should also be completed at two time points by personnel responsible for patient follow-up: 1) time of the first scheduled follow-up of the first prospective patient and 2) end of Registry.

8.0 Patient Management

There are no additional follow-up requirements once a patient has been withdrawn from the Registry. The appropriate case report forms can be completed to document withdrawal of any patient from the Registry.

Patients may be withdrawn from the Registry subsequent to enrolment for a variety of reasons including:

- Investigator decision to remove patient from Registry;
- Patient is lost to follow-up despite best effort to locate patient;
- Patient declines further participation in the Registry after being informed of the risks associated with the system under investigation.

